11.6.3 Summary of MRI Safety Evaluations

MRI safety evaluations will be summarized and compared between each ABBV-8E12 dose and placebo based on MRI evaluations in the double blinded period. The summaries include the number and percentage of subjects pertaining cerebral edema, micro- and macro-haemorrhages, white matter hyperintensities (ARWMC score) across visits; number and percentage of subjects with presence and increasing severity of cerebral edema; number and percentage of subjects with new micro- and macro-haemorrhage lesions; number and percentage of subject with white matter hyperintensities change (ARWMC score) from previous time point. Descriptive statistics (mean, median, minimum, maximum) of number of new micro- and macro-hemorrhages or new lesions, as well as changes in ARWMC score in the double-blinded period will be presented.

12.0 Pharmacokinetic Analysis

12.1 Determination of Values of Pharmacokinetic Parameters

C_{\max} for a dose interval will be the maximum observed concentration after the beginning of infusion of the dose and before the beginning of infusion of the next dose. T_{\max} will be the time of C_{\max} relative to the beginning of infusion. The values of C_{\max} and T_{\max} will be considered missing if there is no measurement from a sample obtained before 3 hours after the end of infusion.

AUC for a dose interval will be obtained using straight lines between adjacent concentrations for times before 4 hours after the end of infusion. An exponential curve will be used between the last time point of measurement before 4 hours after the end of infusion and the first time point of measurement after 4 hours after the end of infusion,

and an exponential curve will be used between adjacent time points of measurement in the dose interval that come after this. Actual times relative to the beginning of infusion will be used in the calculation of AUC.

The scheduled length of the first and fifth dose intervals is 336 hours and 672 hours, respectively. If the actual length of a dose interval differs from the scheduled length by more than an hour, a value for the ABBV-8E12 concentration at the scheduled end of the dosing interval (336 hours or 672 hours after the start of infusion of the dose at the beginning of the dose interval) will be imputed. In this case, the AUC will be calculated using the imputed value at the scheduled end of the dosing interval. The imputed value will be obtained from interpolation with, or extrapolation of, the exponential curve defined by the last two concentration measurements in the dosing interval.

For the first dose interval, the concentration at the beginning of infusion of the dose will be assumed to be 0 even if the scheduled pre-dose blood sample is mistakenly obtained after the beginning of infusion. For the fifth dose interval, the concentration of the pre-dose sample will be used as the concentration at the beginning of infusion of the dose provided that the blood sample is obtained in the 30 minute interval before the beginning of infusion. If the blood sample is obtained earlier than 30 minutes before the beginning of infusion, for the calculation of AUC the concentration at the beginning of infusion will be the $C_{obs} \times e^{-\beta t}$, where C_{obs} is the reported measurement for the pre-dose concentration, β is the rate constant determined from the exponential curve defined by the last two concentrations in the fifth dose interval and t the length of the time interval between the pre-dose blood sample and the beginning of infusion. If the pre-dose sample for the fifth dose interval is mistakenly obtained after the beginning of infusion of the dose, a value for the concentration at the beginning of the dose interval (beginning of infusion) must be imputed unless the sample was obtained within a very few minutes of the beginning of infusion (< 15 minutes). The data of other subjects in the same treatment group who have values for the concentrations at the beginning of the fifth dose interval, the beginning of the fourth dose interval and the end of the fifth dose interval may be used to obtain a linear regression model for the concentration at the beginning of the fifth dose

interval, with the concentrations at the beginning of the fourth dose interval and the end of the fifth dose interval as explanatory (predictor) variables. The missing value may be replaced by the predicted value from the regression model.

12.2 Tabulations and Summary Statistics

For the data of Cohort 1, serum concentrations of ABBV-8E12 and pharmacokinetic parameter values will be tabulated for each subject and each dose level, and summary statistics will be computed for each sampling time and each parameter by dose level. Also, for the serum concentration data of all subjects (Cohort 1 and Cohort 2), summary statistics will be provided for each scheduled time of sampling with breakdown by dose level.

CSF concentration data after the fifth dose (for subjects in Cohort 1) and the final dose will be tabulated and summarized by dose level.

Summary statistics will consist of: number of observations (n), mean, standard deviation, coefficient of variation as a percentage (quotient of standard deviation and mean, multiplied by 100), minimum, median and maximum. In addition, the geometric mean will be given for C_{max} and AUC.

12.3 Model and Tests

Unless stated otherwise, hypothesis tests will be performed at significance level 0.050.

Change in Concentration with Repeated Dosing

The concentration data of the planned pre-infusion sampling times of Cohort 2 (Days 15, 29 and 85 plus Weeks 24 and 36) will be analyzed to investigate change in serum concentration over time. The data of Cohort 1 and Cohort J1 will also be included in this analysis except for Day 29. The logarithmic transformation will be used unless the data show that the logarithm has substantial non-symmetry (e.g., magnitude of skewness coefficient > 1.0) while untransformed concentration or another transformation has an approximately symmetric distribution. A MMRM analysis will be performed. The model

will have fixed effects for dose level, geographical region (as identified in Section 10.7), classification by time, interaction of dose level and time and the interaction of region and time. The subjects will be viewed as a random sample, and an appropriate structure will be selected for the covariance matrix of the observations from a subject. If the statistic on the interaction of region and time is not significant at level 0.050, that term will be removed from the model. The concentration central value estimate versus time curves for the two dose levels will be plotted on the same graph, with the estimate of the central value for a dose level at a given time being the back transformation of the SAS least squares mean for the transformed data.

Dose Proportionality

Analyses to address the issue of dose proportionality will be performed on the combined data of Cohort 1 and Cohort J1. An analysis will be performed on each of dose normalized C_{\max} and dose-normalized AUC for each of the first dose interval (2 weeks in length) and the dose interval beginning at Day 85 (4 weeks in length). An analysis will also be performed on dose-normalized C_{trough} at Week 16. The logarithmic transformation will be employed for C_{\max} and AUC and will likely be used for C_{trough} . An analysis of covariance (ANCOVA) will be performed for each exposure variable, with the greater emphasis on the dose interval that begins at Day 85. Subjects will be classified by dose level and geographical region, and body weight will be a covariate. The initial model will include a term for the interaction of dose level and region, but this term will be removed from the model if the statistic for it is not significant at level 0.050. Other variables such as age and sex that might explain some of the variability among subjects will be considered. A necessary condition for such a variable to be included in the final model is that the regression coefficient be significant at level 0.100. The dependence among explanatory variable candidates will also be considered when selecting the final model. Within the framework of the final model, the hypothesis of no difference between the means of the two doses (main effects for the two doses) will be tested. If the statistic on the interaction of dose level and region is significant at level 0.050, the test will be performed for each region separately within the framework of the final model.

Comparison of the Geographical Regions with Respect to Drug Exposure Variables

The data set for this analysis will be the same as that for the analysis to address the issue of dose proportionality. Because Cohort 1 and Cohort J1 have no data from Canada, European countries or Australia, the analysis provides a comparison of the Japan region to the North America region (US). The model will be the same as the final model for the analysis on dose proportionality with the one exception that body weight will not be included as a covariate. Assuming that the logarithmic transformation is employed, the estimates of the central values for the four combinations of region and dose level (on the original scale and without dose normalization) will be provided by exponentiation of the corresponding SAS least squares means, followed by multiplication of the respective dose levels.

Within the framework of the final model, the hypothesis of no difference between the means of the two regions (main effects for the two regions) will be tested. The estimate of the ratio of the central values (a composite value for the two dose levels) of the two regions will be provided by exponentiation of the difference of the SAS least squares means for the two regions. If the statistic on the interaction of dose level and region is significant at level 0.050, the test will be performed for each dose level separately within the framework of the final model, and the corresponding estimate of the ratio of region central values provided by exponentiation of the difference of least squares means for the two regions for the given dose level.

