Subjects in Cohort J1 will be enrolled at least 2 days apart and will be confined for a minimum of 24 hours following their first infusion. Subjects will have another study visit to be assessed for safety 2 days after the first infusion. From the second to the fourth infusion, Cohort J1 subjects will be observed on-site for at least 2 hours following each infusion of study drug.

Subjects in Cohort 2 will be observed on-site for at least 2 hours following each of the first 4 infusions of study drug. Following the 4th infusion, all subjects in all cohorts will be observed on-site for at least 30 minutes after the end of the infusion.

This study will utilize a DMC consisting of at least 2 external clinicians, at least 1 external statistician, and at least 1 external pharmacokineticist. The DMC will review unblinded safety and efficacy data and make recommendations to the Sponsor based on the totality of available clinical data. The DMC memberships, responsibilities and operating logistics will be documented in a charter that will be prepared prior to the first DMC review meeting.

Methodology (Continued):

Safety and tolerability will be monitored throughout the study, specifically including conditions associated with infusions in general, and infusion reactions. The first 39 subjects enrolled into the study will be represented as Cohort 1 (30 subjects) and Cohort J1 (9 subjects) in this protocol, while the subjects enrolled subsequently to Cohort 1 and Cohort J1 will be represented as Cohort 2. More frequent PK sampling and safety monitoring by the DMC will be conducted for Cohort 1 and Cohort J1 subjects.

Diagnosis and Main Criteria for Inclusion/Exclusion:

Main Inclusion Criteria:

- Male or female subject with age 40 years or greater at the time of signed consent.
- Meets the following criteria for possible or probable progressive supranuclear palsy (Steele-Richardson-Olszewski Syndrome):
 - gradually progressive disorder, with age at disease onset greater than or equal to 40 years
 - either or both of the following two items are met:
 1. vertical supranuclear gaze palsy
 2. slowing of vertical saccades AND postural instability with falls within the first 3 years of PSP symptoms

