The change in serum concentration across time will be considered in an analysis of C_{trough} data, with the logarithmic transformation used if appropriate. The pre-infusion concentration data for Days 15, 29 and 85, plus Weeks 24 and 36 will be analyzed with a MMRM model. For measures of exposure, an analysis of covariance will be performed on dose normalized parameters of Cohort 1 and Cohort J1. It is anticipated that the logarithmic transformation will be employed. Subjects will be classified by dose level and region, and the initial model will contain an effect for the interaction of dose level and region. Body weight will be a covariate. The model may have other covariates. The hypothesis of dose proportionality will be tested within the framework of the model.

Population pharmacokinetic analyses will be performed using the actual sampling time relative to dosing. Pharmacokinetic models will be built using a non-linear mixed-effect modeling approach with the NONMEM software (version VII, or higher version). The structure of the starting pharmacokinetic model will be based on the pharmacokinetic analysis of data from previous studies and Cohort 1 and Cohort J1 of this study. Apparent CL and apparent volume of distribution (V) of ABBV-8E12 will be the pharmacokinetic parameters of major interest in the NONMEM analyses. If necessary, other parameters, including the parameters describing absorption characteristics, may be fixed if useful in the analysis.

CSF concentration data after the fifth dose (for subjects in Cohort 1 and Cohort J1) and the final dose will be summarized by dose level.

Immunogenicity:

The anti-drug antibody titers will be tabulated by dose level and summarized as appropriate.

Biomarker:

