Analyses to address the issue of dose proportionality will be performed on the combined data of Cohort 1 and Cohort J1. An analysis will be performed on each of dose normalized C_{\max} and dose-normalized AUC for each of the first dose interval (2 weeks in length) and the dose interval beginning at Day 85 (4 weeks in length). An analysis will also be performed on dose-normalized C_{trough} at Week 16. The logarithmic transformation will be employed for C_{\max} and AUC and will likely be used for C_{trough} . An analysis of covariance (ANCOVA) will be performed for each exposure variable, with the greater emphasis on the dose interval that begins at Day 85. Subjects will be classified by dose level and region, and the initial model will contain an effect for the interaction of dose level and region. Body weight will be a covariate. Other variables such as age and sex that might explain some of the variability among subjects will be considered for inclusion as covariates. A necessary condition for such a variable to be included in the final model is that the regression coefficient be significant at level 0.100. The dependence among explanatory variable candidates will also be considered when selecting the final model. If the test statistic for interaction of dose level and region is not significant at level 0.100 for at least one of the three exposure variables for the dose interval beginning at Day 85, the effect for interaction will be removed from the model for all variables for both dose intervals. For each of the two dose intervals for each variable, the hypothesis of no difference between the dose level main effects will be tested (a composite assessment across the regions) within the framework of the final model. If the final model contains an effect for interaction of dose level and region and if the test statistic on interaction is

significant at level 0.100, the hypothesis of no difference between the dose levels will be tested for each region within the framework of the final model.

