4.2 Study Design

This Phase 2, randomized, double-blind, placebo-controlled, multiple dose, multicenter study will consist of a screening period of up to 8 weeks (56 days), a 52 week double-blind treatment period, and a post-treatment follow-up period of approximately 20 weeks following last study drug administration (including those subjects who prematurely discontinue from treatment, decline to participate in or do not qualify for participation in a long term extension [LTE] study). The study is planned to be conducted at approximately 60 sites in the US and outside of the US. Approximately 330 subjects who are at least 40 years of age with PSP will be eligible to participate in the study according to the selection criteria.

Upon completion of screening and baseline procedures, eligible subjects will be randomized to one of the two ABBV-8E12 dose arms (2000 mg or 4000 mg) or placebo in a 1:1:1 ratio. Subjects will enter the Treatment Period of the study on Day 1 and receive their first infusion of study drug. During the first 4 weeks, subjects will have

3 study drug infusions; the first on Day 1, the second on Day 15, and then on Day 29; thereafter, subjects will return to the study site every 28 Days for their the schedules for study drug infusion, blood collection, study procedures and assessments as outlined in the Study Activities Table ([Table 1](#) and [Table 2](#)). This dosing schedule (with one additional dose delivered on Day 15) is intended to enable subjects to reach steady-state levels of ABBV-8E12 in plasma as soon as reasonably possible in order to maximize the potential benefit to subjects during the treatment period. This study will utilize a Data Monitoring Committee (DMC) consisting of 4 external clinicians, 1 external statistician and 1 external pharmacokineticist. The DMC will review unblinded safety and efficacy data and make recommendations to the Sponsor based on the totality of available clinical data. The DMC memberships, responsibilities and operating logistics will be documented in a charter that will be prepared prior to the first DMC review meeting.

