5.2 Variables Used for Stratification of Randomization

Subject randomization is stratified by study site except for Japanese subjects who are randomly assigned to three groups with 1:1:1 ratio within Japan.

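### Inference on dose proportionality is a test of no difference alone, with no dose ratio or interval to show which modest departures remain possible

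*SAP*

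**What the plan says.** SAP 12.3 (Dose Proportionality) fits an ANCOVA to dose-normalised C_max and AUC for the first dose interval and for the interval starting at Day 85, and to dose-normalised C_trough at Week 16. C_max and AUC are log-transformed; C_trough probably will be. Dose level and region are factors and body weight is a covariate. The inference is that "the hypothesis of no difference between the means of the two doses (main effects for the two doses) will be tested", by region if the dose-by-region term is retained.

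Protocol 8.1.7.2 has the same test: "the hypothesis of no difference between the dose level main effects will be tested (a composite assessment across the regions". The synopsis puts it as "The hypothesis of dose proportionality will be tested within the framework of the model", which makes proportionality the null hypothesis.

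Neither document plans a dose-normalised ratio of the two doses, a confidence interval for it, a power statement or a rule for reading a non-significant result. The next part of SAP 12.3 compares regions on the same data with the same model apart from body weight, and there it does commit to a ratio: "The estimate of the ratio of the central values (a composite value for the two dose levels) of the two regions will be provided".

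**The concern.** When proportionality is the null hypothesis, a p value can count against it but cannot show how close to proportional the data are. A non-significant result may mean that exposure is close to proportional, or that the sample is too small and variable to show otherwise. Only an interval for the dose ratio separates these, and it is not planned. The ratio is the quantity of interest here, yet it is promised for regions and not for doses. The SAP does specify 95% intervals for its safety ANOVAs (11.3.1, 11.4.1, 11.5.1 and 11.6.2), but none in the pharmacokinetic section.

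The stakes are moderate. Multiple-dose pharmacokinetics is a secondary objective, and protocol 5.6.4 assumed linear pharmacokinetics when it simulated steady-state exposure at 2000 and 4000 mg. How far the multiple-dose data support that assumption is a fair question for the study report.

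**Working it through.** **Inputs**

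- Analysis set: "Analyses to address the issue of dose proportionality will be performed on the combined data of Cohort 1 and Cohort J1" (SAP 12.3).
- Size: "The first 39 subjects enrolled into the study will be represented as Cohort 1 (30 subjects) and Cohort J1 (9 subjects" (protocol synopsis). 30 + 9 = 39. The documents state no power or precision for this analysis, so this is the only figure of theirs to reproduce.
- Allocation: "randomized to one of the two ABBV-8E12 dose arms (2000 mg or 4000 mg) or placebo in a 1:1:1 ratio" (SAP 4.2). 39 / 3 = 13 per arm, so 26 on active drug.
- The 13 is approximate. "Subject randomization is stratified by study site except for Japanese subjects" (SAP 5.2), so the first 30 subjects need not split 10/10/10. Early discontinuation would lower the number at Day 85 and Week 16.
- Level: 0.050 (SAP 12.3). Two-sided is assumed; SAP 6.1 states it for efficacy and safety only.
- Residual df: intercept, dose, region (two regions in these cohorts) and body weight are 4 parameters, so 26 − 4 = 22.
- CV: not in the documents. Assumed 30%, range 20% to 40%, meaning the residual CV after adjustment for region and weight.

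**Formulas**

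- Log-scale SD: s = √ln(1 + CV²)
- Standard error of the log ratio: SE = s × √(2/13) = 0.392 s
- Noncentrality: δ = |ln(ratio)| / SE; power from the noncentral t with 22 df and critical value 2.074
- 90% CI for the ratio: estimate × or ÷ exp(1.717 × SE)

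**Example at CV 30%.** s = √ln(1.09) = 0.294 and SE = 0.115. Since |ln 0.80| = ln 1.25 = 0.223, δ = 0.223 / 0.115 = 1.94 and power is 46%. For a 1.5-fold departure, δ = 0.405 / 0.115 = 3.52 and power is 92%. The interval factor is exp(1.717 × 0.115) = 1.22.

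| Assumed CV | SE | Power, ratio 0.80 or 1.25 | Power, 1.5-fold | Ratio detectable with 80% power | 90% CI factor | CI around 1.00 |
|---|---|---|---|---|---|---|
| 20% | 0.078 | 78% | 99.9% | 1.26 | 1.14 | 0.88–1.14 |
| 30% | 0.115 | 46% | 92% | 1.40 | 1.22 | 0.82–1.22 |
| 40% | 0.151 | 29% | 73% | 1.56 | 1.30 | 0.77–1.30 |

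Direction matters when the departure is given as a percentage: 0.80 is a 20% shortfall or, inverted, a 25% excess. A 20% excess (ratio 1.20) is smaller on the log scale, and its power is 61%, 33% and 21% at the three CVs.

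**Sensitivity.** If only 11 per dose have Day 85 data (an assumption), power against 0.80 or 1.25 is 71%, 39% and 25%. If the dose-by-region term is retained, the Japan comparison is about 3 against 3 (9 / 3 per arm), and its 90% CI factor is 1.32, 1.51 and 1.72.

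**The case against.** Four points can be made for the plan.

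- **The size of any dose difference will be visible.** SAP 12.2 gives geometric means of C_max and AUC by dose. The regional comparison gives back-transformed central values for each region and dose. The repeated-dosing analysis plots central values by dose from all cohorts. This stands: the test is the only inferential step, not the only output. None of these outputs carries an interval, however. SAP 12.2 names Cohort 1 only, although protocol 8.1.7.1 combines it with J1. The regional values come from a model without body weight and are not dose-normalised.
- **No conclusion rule is stated.** A reader might infer that a small, noisy sample will be taken to confirm proportionality. The documents do not say so. The SAP presents the analyses as addressing the issue, and the synopsis says only that the hypothesis will be tested.
- **The test is not uninformative.** A reader might infer that non-significance says little at all. With 92% power against a 1.5-fold departure at CV 30%, that is too strong. The gap concerns modest departures, and its size depends on an assumed CV.
- **Little hangs on the result.** The secondary objective does not name dose proportionality, and no dosing, stopping or efficacy decision is tied to this test. The protocol's introduction reports dose-proportional AUC after single doses from 2.5 to 50 mg/kg. This is why the point is minor. Those are single-dose data, and population pharmacokinetic analysis is conditional and outside the SAP (SAP 3.0).

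**Conclusion.** The point holds as a minor one about method and reporting. Formal inference on dose proportionality is a test of no difference between dose-normalised means at 0.050, with no dose ratio or interval. At about 13 per active dose and CV 30% or more, the test misses a true ratio of 0.80 or 1.25 more often than it finds it. At CV 20% it finds it about three times in four. Departures of 1.5-fold are detected with high power at CV 20% to 30% and with 73% power at 40%. Non-significance therefore cannot exclude modest departures at moderate or high CV, and a bare p value never shows which departures are excluded.

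These figures rest on the assumed CV, a two-sided test, an even 1:1:1 split and full data at Day 85 and Week 16.

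**What to change.** In SAP 12.3, from the ANCOVA already planned:

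- Report the dose-normalised ratio (4000 mg / 2000 mg) with its 90% CI for each of the five analyses: C_max and AUC for both dose intervals, and C_trough at Week 16 if it is log-transformed. Report it by region as well if the interaction is retained.
- Describe dose proportionality by the departures that the interval does and does not exclude.
- State that a non-significant test will not be read as proportionality.

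No acceptance range is needed. With an illustrative range of 0.80 to 1.25 and exact proportionality, the 90% CI would fall inside it with probability of only about 75%, 21% and 2% at CV 20%, 30% and 40%. This sample would often fail such a criterion.

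The cost is a few output lines: exponentiate the least squares mean difference and its limits. No new subjects, samples or models are required. The interval does not make the sample more precise; it reports the precision there is.
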